### 6.1.2 DURATION OF THERAPY

Both arms will continue until 6 hours after randomization. 6 hours was chosen to avoid confounding by patients with overly long ED LOS. At minimum, patients should receive at least one round of treatment. The protocol continues even if patients reach the floor. However, if in the opinion of the investigator, the protocol should not be continued once on the hospital floor, this is allowed and should be marked on the case report form.

## 7 STUDY PROCEDURES AND SCHEDULE

### 7.1 STUDY PROCEDURES/EVALUATIONS

#### 7.1.1 STUDY SPECIFIC PROCEDURES

The table below in section 7.3.7 highlights study specific procedures. Only patients who sign written informed consent will undergo study specific procedures.

---

#### 7.1.2 STANDARD OF CARE STUDY PROCEDURES

Except for the ED phase of management, there will be no other change to standard of care procedures for either treatment arm. Patients will continue to be assessed however, during hospitalization.

## 7.2 LABORATORY PROCEDURES/EVALUATIONS

### 7.2.1 CLINICAL LABORATORY EVALUATIONS

Lab testing will be analyzed by the clinical lab at each respective institution for baseline chemistry and hemoglobin/hematocrit values. This reflects our pragmatic approach. If routine labs are performed clinically within 6 hours of the follow up time-point, these results will be used for study purposes (Table 2). If routine lab work is not drawn, the closest clinical lab draw will be recorded in the eCRF unless already recorded (i.e. the baseline value). NO labs, other than for NTproBNP and hsTnT will be drawn for study purposes. Samples will be stored and shipped to Indiana University at the Clinical and Translational Sciences Laboratory. At quarterly intervals, samples will be analyzed in our core lab, with expertise in clinical lab sampling.

All clinical laboratory test results outside of the reference range will be interpreted in the context of the patient underlying disease state by the Investigator using the following categories:

- abnormal but not a clinically-significant worsening
- abnormal and a clinically-significant worsening

A laboratory test result that has significantly worsened (according to medical judgment) compared with the baseline result will be recorded on the CRF as an adverse event and monitored. An adverse event includes a laboratory or diagnostic test abnormality (once confirmed by repeat testing as needed) that results in the temporary or permanent cessation of treatment, or requires medical treatment or further diagnostic work-up. The AE and SAE reporting period extends to day 5 of hospitalization or discharge, whichever comes first, unless otherwise specified.

A local laboratory will be utilized to analyze screening entry criteria.

### 7.2.2 OTHER ASSAYS OR PROCEDURES

NT-proBNP and hsTnT levels will be analyzed centrally. Roche Diagnostics will provide in-kind support for the cost of analytical testing and reagent support.

### 7.2.3 SPECIMEN PREPARATION, HANDLING, AND STORAGE

All human body fluids should be handled as potentially infectious. Personal protective equipment should be used. If any blood is collected using an indwelling catheter at least 0.5mL discard sample will be taken if the catheter was flushed with saline.

2 aliquots per sample type per collection = 6 total aliquots

Time Point	Tube Type	Blood Volume
T0 = 0 hour (Baseline)	Serum Separator	One tube, ~ 4cc
	Lithium Heparin	One tube, ~ 4cc
	EDTA Plasma	One tube, ~ 4cc
	Serum Separator	One tube, ~ 4cc

T1 = Day 7 or discharge +/- 24 hours	Lithium Heparin	One tube, ~ 4cc
	EDTA Plasma	One tube, ~ 4cc

**Samples will be collected in the following order:**

1. Serum separator
2. Lithium heparin
3. EDTA plasma

Every attempt to collect both samples should be made.

Specimens must be processed within 3 hours of collection and no later than 4 hours. This includes collection, centrifuge, aliquot, and then frozen. Samples should be held at 4 degrees Celsius until processed.

Standard venipuncture techniques or other standard blood collection methods will be used. These must be in accordance with institutional standards, policies, guidelines, recommendations, and requirements.

After collection, please use the following instructions for guidance. If there is doubt, the tube manufacturer instructions are the final arbiter for any disputes.

*Serum:* After collection, let sit at room temperature for ~30 minutes to allowing clotting to occur. Then centrifuge at 1000-1300 g for 10-15 minutes at room temperature.

*Lithium Heparin plasma:* After collection, invert tube gently 10 times to ensure mixing with anti-coagulant. Then centrifuge at 1000-1300 g for 10-15 minutes at room temperature.

*EDTA:* After collection, invert tube gently 10 times to ensure mixing with anti-coagulant. Then centrifuge at 1000-1300 g for 10-15 minutes at room temperature

All tubes should be removed from centrifuge immediately upon completion and when safe to do so. Remove at least 0.5cc of supernatant for each aliquot, with 2 aliquots per tube. DO NOT MIX or POOL supernatant from separate pools together.

Each aliquot must be stored in appropriate cryovials, for storage at -20degrees Celsius or colder. Cryovials are pre-labeled without PHI.

Freezers must have temperature logs available for review.

---

#### 7.2.4 SPECIMEN SHIPMENT

Frozen biomarker specimens will be batch shipped on a quarterly enrollment basis on Dry Ice. A specimen shipping form will accompany all shipments with a copy kept at the site. All samples should be stored at -20C or lower until the sample is shipped. Whole blood will be collected, processed (centrifuged locally) and stored appropriately for shipment to Indiana University (IU) for central processing.

All personnel responsible for shipping of specimens are certified by their respective institutions. IU will provide the minimum required procedures. Shipping procedures are defined by the appropriate CTSL standard operating procedures. Shipping services, if required, will include documentation, QC, manifest creation and dry ice (if required). Detailed shipping information will be sent to each site prior to shipment.

### 7.3 STUDY SCHEDULE

---

#### 7.3.1 SCREENING

A signed and dated informed consent form will be obtained before any study-specific screening procedures are performed. Results of evaluations obtained as part of routine medical care, which are performed prior to obtaining informed consent, may be used in place of the protocol-specified evaluations. Patients will acknowledge and agree to the use of this information for the study by giving informed consent.

At the Baseline Visit, patients will be assigned by the Internet Web-based Randomization System (IWRS) a unique permanent identification number (referred to as the patient identification number) such that all randomized patients from each center are given consecutive identification numbers by the IWRS in successive order of inclusion. We will utilize the REDCap randomization module. (NOTE: thus each patient will have two ID's – 1) generated by IWRS and 2) blood specimen label)

Prospective study patients will have presented to the hospital for urgent therapy for AHF. Potential patients will be identified either en route to or upon arriving at the ED/hospital. Routine assessments associated with usual patient care may be used for the purposes of screening and may be completed in any order. Study specific procedures must be completed only after Informed Consent is obtained.

Randomization will occur within three hours of patient's arrival to a room within the ED where they can be seen by a physician or the first time AHF treatment is given. Waiting room time does not count against these three hours.

The following procedures will be performed prior to or during Screening:

- Obtain written informed consent (must be performed as the first study-specific procedure)
- Review of prior medical history
- Review of prior and concomitant medications
- Physical examination (including height and weight when reasonably possible)
- Vital signs measurements (includes systolic and diastolic blood pressures, heart rate, body temperature, oxygen saturation reading and respiratory rate)
- 12-Lead Electrocardiogram
- Chest X-Ray (this is not a requirement however, for inclusion)
- Blood collection for local laboratory tests, including BNP or NT-proBNP, and pregnancy test if applicable.
- Inquiry about Adverse events

---

### 7.3.2 ENROLLMENT/BASELINE

Patients who continue to fulfill all of the inclusion/exclusion criteria will be randomized no later than 3 hours after the first recorded time stamp when patient placed in a room to be seen by a provider. Waiting room time does not count. Randomization will occur via central IWRS system.

---

### 7.3.3 FOLLOW-UP & FINAL STUDY VISIT

Patients will be followed for a maximum of 90 days post-discharge. There will be NO further in-person visits once discharged. Patients will be called however at 30 and 90 days post-discharge ((+) 30 business days or at the discretion of the local site PI to assess vital status and re-hospitalizations or ED visits.

---

### 7.3.7 SCHEDULE OF EVENTS TABLE

Schedule of Events	Screening	Day 1 T00	Day 1 T02-04	Day 1 T06	Day 2-6 T24-D6	Day 7 or D/C*	30 & 90 day follow up	Quarterly
Informed consent (I/E)	X							
Medical History	X							
Medication history	X							
Clinical Assessment #		X	X	X	X	X		
Body Weight, height, Vital Signs	ED SOC	VS only	VS only	VS only	BW/VS only	BW/VS only		
Labs: Electrolytes, hematology, NP, eGFR, Troponin	ED SOC							
NT-proBNP / hsTroponin (for central lab processing)		X				X		
12-lead ECG	ED SOC							
CXR	ED SOC							
LUS B-lines 8 zone	X (LUS T00)		X	X	X	X		
LUS Guided AHF Management or Usual Care		X	X	X				
Lab draw: eGFR, Hgb/Hct ^		X				X*		
Prep and Storage of Samples		X				X		
eCRF/data collection/verification		X					X	

Assessment of AE/SAE's							X	
Phone follow-up Vital Status							X	
Batch shipment of samples								X
Subject payment		X					X	

SOC = standard of care, ED = Emergency Department, I/E = inclusion, exclusion, CV = cardiovascular, LUS = lung ultrasound, BW = body weight, NP = natriuretic peptide ^if collected as part of standard of care, will use that result. The last collected result will be used if not drawn on or close to discharge \*Day 7 or discharge, whichever comes first. #As documented by clinician during inpatient stay or per form for ED phase

Further detail regarding timing of assessments: [NOTE: given clinical circumstances (i.e. left the ER for a test, discussion with consultant, etc) – the SITE PI has final discretion to continue to image a patient before or after the allotted window. This time MUST be recorded in the eCRF]

- T00: initial LUS scan (in ED for screening and eligibility)
- T02: 2-4 hours after initial treatment (in ED) (+/- 30 minutes)
- T06: 2-4 hours after T02 or pre-ED discharge, whichever comes first (+/- 60 minutes)
- HD2: 24 hours after initial scan (Day 2) (+/- 6 hours)
- HD3: 48 hours after initial scan (Day 3) (+/- 8 hours)
- HD4: Day 4 (anytime during day)
- HD5: Day 5 (anytime during day)
- HD6: Day 6 (anytime during day)
- HD7: Day 7 (anytime during day)

\* NTproBNP/hsTnT blood draw. This should occur within 6 hours of randomization. Ideally, the blood draw should occur as soon as possible after randomization, preferably within 3 hours.

\*\* For vital signs during hospitalization. The nearest vital signs to the LUS exam will be captured.

^HD = Hospital day

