Common Risks. The greatest risks are not necessarily different than those already associated with these therapies. However, the risk may or may not be increased due to use of these treatments in a guided protocol strategy. For IV loop diuretics, commonly encountered risks include potential acute kidney injury (AKI) and over diuresis leading to hypovolemia. Electrolyte abnormalities may also occur. Per routine standard of care at each of the sites, electrolytes are routinely checked during the initial 24-48 hours of treatment. These will be recorded. However, should no further electrolytes be measured after admission, a pre-discharge lab draw will be performed. While AKI may occur, more recent data suggests that failure to decongest is associated with greater risk for adverse outcomes than transient AKI. To add a margin of safety, only patients with an eGFR  $\geq 45$  will be enrolled. Finally, we will assess eGFR prior to discharge (if measured as part of standard of care) to better understand whether our proposed strategy-of-care is associated with worsening renal function. For nitrates, the greatest risk is hypotension. All patients will have IV access for fluids, if needed. Of note, the ESC guidelines allow for the potential use of IV nitrates in patients with a SBP  $> 110$ mmHg and only recommend avoiding them if the SBP is  $< 110$  mmHg. Another common side effect is headache, which will be treated with Tylenol or other non-narcotic analgesic medication. Use of NIV is both safe and effective. Greatest risks are those of aspiration in those with altered mental status. However, emergency physicians are well versed in the use of NIV as well as endotracheal intubation. No patients who are unable to protect their airway will be placed on NIV. Patients may also complain of claustrophobia or discomfort with the tight fitting mask. Attempts to adjust accordingly will be made. Anecdotally, patients feel significantly better and usually the improvement outweighs the discomfort. Other issues such as skin necrosis from long-term use of NIV does not apply to the short-term use of NIV.

An unknown risk is whether or not our treatment strategy is associated with myocardial injury. Thus, we will measure hsTnT at both baseline and pre-discharge to ascertain the incidence of myocardial injury.

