### 10.4.3 ANALYSIS OF THE PRIMARY EFFICACY ENDPOINT(S)

The comparison of binary endpoints (B-lines < 15) will be performed using Chi-square or Fishers exact test, as appropriate.

Potential covariates will also be considered in a logistic regression setting to improve precision, which includes baseline co-morbidities, baseline medications (in particular guideline recommended therapies) in-hospital medications, baseline renal function, serum sodium, natriuretic peptide levels, troponin levels, renal function, baseline blood pressure, and discharge medications. Variables such as physical exam, other vital signs, and hemoconcentration may also be included. For NT-proBNP, a percent change greater than 30% and its association with the primary endpoint will be analyzed. This is based on previous work suggesting a 30% change was a key discriminatory threshold for mortality. For hemoconcentration, any increase in value in both hematocrit and hemoglobin during hospitalization will be considered positive. These covariates are known markers of risk and are standard of care assessments for the vast majority of AHF admissions. Covariates with univariately significant association with the outcome will be included together with the treatment indicator in a logistic regression model. Due to limited sample size, we will limit the number of covariates (including treatment indicator) such that there is 10 events per covariate.

---

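### The discharge eGFR and Hgb/Hct rule takes the last collected value without requiring that it post-date baseline, so change can be set to zero in patients with no later draw

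*Combined protocol and SAP*

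**What the plan says.** The schedule of events (section 7.3.7) has a row for eGFR and Hgb/Hct with two draws, one at T00 and one at day 7 or discharge. Its footnote gives the fallback for the second: "The last collected result will be used if not drawn on or close to discharge". No maximum age is given, and the value need not come after baseline or after treatment.

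Section 7.2.1 covers the same situation in other words. A routine result near the time-point is accepted: "If routine labs are performed clinically within 6 hours of the follow up time-point, these results will be used for study purposes". Failing that, "the closest clinical lab draw will be recorded in the eCRF unless already recorded (i.e. the baseline value". The same section also states "NO labs, other than for NTproBNP and hsTnT will be drawn for study purposes".

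Section 2.3.1 makes the discharge eGFR depend on routine care ("we will assess eGFR prior to discharge (if measured as part of standard of care") and gives its purpose: to learn "whether our proposed strategy-of-care is associated with worsening renal function". Yet it also says "should no further electrolytes be measured after admission, a pre-discharge lab draw will be performed", and its last paragraph foresees additional blood draws that cover eGFR and Hgb/Hct.

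Three later parts of the plan rely on these values. Table 3 in section 4.2.2 lists biomarker change from presentation to pre-discharge. Section 10.4.3 defines hemoconcentration: "any increase in value in both hematocrit and hemoglobin during hospitalization will be considered positive". Section 10.4.4 compares B-lines with eGFR and hemoglobin/hematocrit, among other markers.

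**The concern.** A last-value rule with no post-baseline condition can make a patient's first measurement serve as the last one too. If the ED draw is the only one, it is literally the last collected result, and change is zero by construction and not by observation.

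Three things follow for such a patient:

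- Worsening renal function cannot be seen on this measure. Section 2.3.1 lists acute kidney injury among the common risks of IV loop diuretics, and section 6.1.1 can give the two arms different diuretic exposure.
- The patient is classed as not hemoconcentrated, because zero is not an increase. Section 10.2 counts hemoglobin/hematocrit among the measures used to judge the superiority or additive value of LUS, so artificial zeros would blur that comparison.
- The value looks complete. Section 10.4.6 plans observed-data analysis, multiple imputation and sensitivity models, but none of them acts on a cell that has already been filled.

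The trial is unblinded (section 10.6.1) and these draws follow routine care, so the chance of a repeat draw could differ by arm. Nothing in the documents shows that it does.

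**Working it through.** The plan gives no figure that depends on this rule, so there is none to reproduce. The check compares the texts and then illustrates the size.

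**1. May baseline stand in for discharge?** The footnote in 7.3.7 neither permits nor forbids it. The exception in 7.2.1 can be read in two ways:

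- A baseline value already on file is not entered again as follow-up, so the discharge value stays missing. This is the more natural reading.
- A baseline value already on file serves, and needs no second entry.

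Under the first reading 7.2.1 leaves a blank, while 7.3.7 still says to use the last result. Two sites could code the same patient differently, one as zero change and one as missing.

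**2. Can a patient have only a baseline value?**

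| Source | Implication |
|---|---|
| 7.2.1, and the note to the trial schematic | Yes: only NT-proBNP and hsTnT are drawn outside standard of care |
| 2.3.1, on eGFR | Yes: measured before discharge only if part of standard of care |
| 2.3.1, on electrolytes | Less likely: routine checks in the first 24-48 hours, and a pre-discharge draw if none follow admission |
| 2.3.1, last paragraph | Less likely: additional draws foreseen for eGFR and Hgb/Hct |

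The documents do not agree.

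**3. Which patients are affected?** Change is forced to zero only where no later draw exists. A carried mid-stay value is a real measurement after baseline. It can miss later worsening, or overstate it if a transient fall in eGFR has recovered by discharge.

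**4. Illustrative size.** Let w be the true rate of worsening and f the share whose discharge value is the baseline value. If worsening is independent of being retested:

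recorded rate = w × (1 − f)

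Both inputs are assumptions: w = 20%, f from 5% to 30%. Counts use 130/2 = 65 patients per arm, so the true count is 65 × 0.20 = 13.0.

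| f | Recorded rate | Recorded cases of 65 |
|---|---|---|
| 5% | 0.20 × 0.95 = 19% | 12.35 |
| 10% | 0.20 × 0.90 = 18% | 11.7 |
| 20% | 0.20 × 0.80 = 16% | 10.4 |
| 30% | 0.20 × 0.70 = 14% | 9.1 |

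**5. Effect on an arm comparison, again with assumed rates.** Take true rates of 15% and 30%, a difference of 15 points.

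- f = 10%, 20% or 30% in both arms: the difference becomes 13.5, 12.0 or 10.5 points (15 × 0.90, 15 × 0.80, 15 × 0.70).
- f = 10% in the 15% arm and 30% in the other: 30 × 0.70 − 15 × 0.90 = 7.5 points.
- f = 30% in the 15% arm and 10% in the other: 30 × 0.90 − 15 × 0.70 = 16.5 points.

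Equal f shrinks a true difference. Unequal f can shrink it further or enlarge it.

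**6. What coding as missing does.** Under the same independence assumption, the rate among those retested is w × (1 − f)/(1 − f) = w. For example, with f = 25%, 0.15/0.75 = 20%. The artefact disappears. If clinicians retest selectively, this equality fails.

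**The case against.** A reader might infer that the footnote instructs sites to use the baseline value, that renal worsening is therefore understated, and that the bias favors the LUS arm. The documents do not support this. The footnote does not mention baseline, and 7.2.1 treats the baseline value as an exception that may well mean leaving the cell blank. A carried mid-stay value can err in either direction. Nothing shows that one arm is discharged earlier or retested less; reversing an assumed imbalance reverses the direction of any bias.

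It can also be said that little depends on these values. Section 10 defines no worsening-renal-function endpoint, threshold or test. Hemoconcentration is a candidate covariate, its wording covers the whole hospitalization and not the discharge value alone, and the primary endpoint is B-lines. Section 7.2.1 separately records a significantly worsened laboratory result as an adverse event. The routine checks and promised draw in 2.3.1 may leave few baseline-only patients.

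Most of this stands and limits the point. Two parts do not remove it. The adverse-event route needs a second result to compare with baseline, so it also misses a patient who was never retested. The draws promised in 2.3.1 cannot be relied on while 7.2.1 rules them out.

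**Conclusion.** The point holds as a defect in a stated data rule. The footnote has no post-baseline condition, and 7.2.1 leaves open whether the ED value may serve as the discharge value. Where it does, zero change is recorded without a second measurement and the missing-data plan is bypassed.

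The number of patients affected and any imbalance by arm are unknown. The figures in the working rest on assumed rates, on assumed shares without a later draw, and on retesting being independent of renal function; they show the mechanism and do not estimate its size. No direction of bias between arms can be claimed. The consequence is confined to a safety descriptor, a covariate and exploratory marker comparisons. The change is worth making because it is nearly free and removes a choice that sites could otherwise make differently.

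**What to change.** - Amend the 7.3.7 footnote so that only a value drawn after the 6-hour treatment period (section 6.1.2) can serve as the discharge value, and never the baseline value. Align 7.2.1 with it.
- Keep later in-stay values, with the draw time recorded. The ±24 hours in 7.2.3 should not be borrowed as a limit: it belongs to the study blood samples, would compete with the 6-hour window in 7.2.1, and would discard genuine post-treatment results.
- Code all other cases as missing and handle them under 10.4.6: observed data, with multiple imputation as a sensitivity analysis.
- Report by arm the number of patients without a post-treatment value.
- Reconcile 2.3.1, 7.2.1 and 7.3.7 on whether a pre-discharge draw is done.

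The cost is one footnote and a few sentences of protocol and analysis text. The downside is some visible missing data, and an observed-case comparison that depends on whom clinicians chose to retest. For that reason the counts by arm and the imputation analysis should accompany it.

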#### 6.1.1 DOSING & DOSE ESCALATION

The algorithm below outlines the treatment protocol.

- All enrolled patients should receive IV furosemide per the protocol box.
  - IF patients already received furosemide prior to the time of enrollment, BRANCH point.
    - Patients in usual care arm will NOT receive any further diuretic.
    - Patients in LUS arm will receive further diuretic to equal 2x single oral dose. For example, if the patient usually takes 80 BID at home, but then already received 40mg at arrival to the ED, if in the LUS arm, would receive an extra 120mg. (200 is the maximum single time dose.)
- Clinical assessments should be recorded irrespective of treatment arm. However, the initial ED LUS assessment will be considered Time 0.

\*IMPORTANT – the clinical assessment alone arm will ALSO have LUS performed – however, these results will NOT be shared with clinical caregiving team

\*\* ALL enrolled patients will be re-assessed at least twice during their ED stay. First re-assessment will occur within 2-4 hours of first TREATMENT. Assessments outside this window are NOT allowed for study purposes unless at the discretion of the investigator. The second re-assessment will occur EITHER 2-4 hours after the first OR prior to discharge. IF the pre-discharge assessment is missed in the ER, this should occur ASAP after arrival to the hospital floor.

NOTE: the maximum dose allowed at any one time of IV Lasix is 200mgIV.

NOTE: For additional IV loop diuretic doses, the options under Restart Algorithm are three options. Clinical/Research team may choose one of the three loop diuretic dose options.

NOTE: for both arms: After each reassessment, the clinical physician will be asked:

1. “In your clinical opinion, is the patient still volume overloaded?” (Yes, No, Not sure)
2. If Yes, then the following question will be asked: “Do you think the patient warrants additional treatment now?”
3. If Yes, then FOR THE CLINICAL ASSESSMENT ARM ONLY: treatment will occur **per the algorithm**. (Patients in the LUS intervention arm will ONLY receive further therapy guided by LUS)

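### The T0 NT-proBNP and hsTnT sample may be drawn at any point in the 6-hour treatment period, so the baseline for biomarker change can be a post-treatment value

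*Combined protocol and SAP*

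**What the plan says.** Section 7.2.3 labels the first research sample "T0 = 0 hour (Baseline", and the schedule in section 7.3.7 places it in the Day 1 T00 column. The footnote to that schedule sets the window: "This should occur within 6 hours of randomization". It then adds a preference: "Ideally, the blood draw should occur as soon as possible after randomization, preferably within 3 hours".

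Section 6.1.2 gives the length of the intervention: "Both arms will continue until 6 hours after randomization". Section 6.1.1 makes early treatment depend on the arm. It has a rule beginning "IF patients already received furosemide prior to the time of enrollment, BRANCH point", after which the LUS arm receives more diuretic and the usual care arm does not. Later treatment follows LUS in one arm and clinical opinion in the other.

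The T0 value has three evident uses:

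- Section 4.2.2 lists, as an exploratory endpoint, biomarker change between presentation and pre-discharge.
- Section 10.4.3 relates a threshold of NT-proBNP change to the primary endpoint: "For NT-proBNP, a percent change greater than 30" (percent).
- Section 2.3.1 calls treatment-related myocardial injury an unknown risk and answers it thus: "we will measure hsTnT at both baseline and pre-discharge to ascertain the incidence of myocardial injury".

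Section 10.4.3 also lists natriuretic peptide and troponin levels as candidate covariates for the primary endpoint, without saying which sample supplies them.

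**The concern.** A baseline should be fixed before the treatment whose effect it helps to measure. Here the permitted window is as long as the intervention. A sample taken late in it already reflects part of the randomized treatment, yet it would be filed and analyzed as hour 0.

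Three results are exposed. Biomarker change would no longer run from presentation. Patients near the 30% NT-proBNP cut could be classed as non-responders because part of their fall came before the draw. A troponin rise during early treatment could be partly absorbed into the baseline, so that the baseline-to-discharge comparison under-counts injury. Because treatment differs by arm after randomization, the distortion can also differ by arm.

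**Working it through.** **1. The plan's own calculation.** Section 10.5 states 81% power with 59 per arm for 25% versus 50%, two-sided 0.05. With pooled variance under the null:

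- SE under the null = √(2 × 0.375 × 0.625 / 59) = 0.0891
- SE under the alternative = √((0.25 × 0.75 + 0.50 × 0.50) / 59) = 0.0861
- Power = Φ((0.25 − 1.96 × 0.0891) / 0.0861) = Φ(0.874) = 80.9%

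The stated figure is reproduced. It concerns B-lines and does not use the blood sample, so nothing below changes it.

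**2. The two windows side by side.**

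| Item | Limit after randomization | Source |
|---|---|---|
| Protocol treatment, both arms | 6 h | 6.1.2 |
| T0 blood draw, permitted | 6 h | 7.3.7 |
| T0 blood draw, preferred | 3 h | 7.3.7 |

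The permitted window covers 6/6 = 100% of the maximum treatment period, and the preferred one 3/6 = 50%. The text contains no requirement that the draw come before the first protocol treatment. The instruction in 7.3.7 that times must be recorded concerns imaging.

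**3. Distance from presentation.** Section 7.3.1 allows randomization up to 3 h after the patient reaches a room "where they can be seen by a physician or the first time AHF treatment is given". On that reading, T0 can fall up to 3 + 6 = 9 h after the first AHF treatment. At most 6 of those hours are protocol treatment. The rest is treatment before enrollment.

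**4. Effect on NT-proBNP change (illustration).** The documents give no kinetics, so the early falls here are assumptions. If the true fall from presentation to discharge is d and the level is already down by g at the draw, the measured fall is 1 − (1 − d)/(1 − g). The true fall needed to read 30% is 1 − 0.70 × (1 − g).

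| g (assumed) | True 30% fall reads as | True 35% fall reads as | True fall needed to read 30% |
|---|---|---|---|
| 5% | 26.3% | 31.6% | 33.5% |
| 10% | 22.2% | 27.8% | 37.0% |
| 20% | 12.5% | 18.8% | 44.0% |

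**5. Effect on hsTnT change (illustration).** If hsTnT has already risen by r at the draw, a true 50% rise reads as 1.50/(1 + r) − 1. For r = 10%, 20% and 30% this gives 36%, 25% and 15%.

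**6. Effect on a between-arm comparison of change (illustration).** If a share f of the arm difference is already present at the draw, the change scores retain 1 − f of it. Take a comparison that would have 80% power at 59 per arm, with the spread of the change scores unaltered. Power becomes Φ((1 − f) × (1.960 + 0.842) − 1.960), which is 71%, 56% and 29% for f = 10%, 25% and 50%. This treats every patient's sample as equally late, so it is an upper picture for each f.

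**The case against.** Six hours is an outer limit. The plan asks for the draw as soon as possible and prefers 3 hours, so many samples may be early. A reader might infer that the biomarker results are biased; the documents support only that they can be. This stands.

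A reader might also infer that the primary model adjusts for a post-treatment variable and so removes part of the effect. Section 10.4.3 does not name the central T0 sample. It describes the covariates as standard-of-care assessments, and sections 7.3.1 and 7.3.7 place local natriuretic peptide and troponin tests at screening. Those local values are at least as natural a reading. The main primary test is an unadjusted chi-square or Fisher test in any case. This stands.

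A third inference is that hsTnT change is the only check on myocardial injury and that any rise in the first 6 hours is lost. Section 2.3.1 fixes no change formula, and pre-discharge hsTnT can be compared between randomized arms with no baseline at all. Screening troponin and adverse-event recording of worsened laboratory values (7.2.1, 8.1.1) add something, though they are local and rest on investigator judgment; section 8.2.3 lists raised troponin as commonly observed. A rise is lost completely only if it ends before the draw. This stands too.

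The 35% example lies just above the 30% cut, where small shifts matter most, and with a 5% early fall it does not cross. That the distortion is larger in the arm that decongests faster is plausible but cannot be shown from the documents.

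The window itself survives these points. It permits a post-treatment baseline, and the plan neither names the local values as the baseline for change nor says how late samples are to be handled; sections 7.2.1 and 7.2.2 send these two markers to a central laboratory.

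**Conclusion.** The point holds as a weakness in the timing rule for T0. The stated window allows the baseline NT-proBNP and hsTnT values to be taken after up to 6 hours of treatment that differs by arm. This can bias the exploratory change from presentation, the 30% NT-proBNP classification and the baseline-to-discharge hsTnT assessment.

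The likely direction is toward smaller changes. That assumes each marker moves in one direction from the start of treatment. The size is unknown: it depends on actual draw times and marker kinetics, and the figures above only show how it scales.

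The unadjusted primary comparison, the 81% power and the sample size of 130 are unaffected. Adjusted models are affected only if the central T0 values are the covariates. The point is worth settling before sampling, because without recorded times the affected samples could not be identified later.

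**What to change.** In section 7.3.7, specify that the T0 research sample is drawn after consent and before the first post-randomization study treatment, wherever this does not delay care. Record the draw time and the first-treatment time in the eCRF, and flag samples drawn after that treatment.

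In section 10.4:

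- State which natriuretic peptide and troponin values are the baseline covariates, and do not use flagged samples as pre-treatment covariates.
- Report biomarker change with and without the flagged samples.
- Add a between-arm comparison of pre-discharge hsTnT and NT-proBNP that does not depend on T0.

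The cost is wording, two time fields, a flag and a sensitivity analysis, with no extra draw or patients. Some baseline values will be flagged or missing, possibly not at random, since patients treated fastest are the likeliest to be affected. For that reason flagged samples should be kept and shown both ways. Sharing the ED clinical draw cannot be relied on: consent must come first (7.3.1), while eligibility needs an eGFR (5.2), so that blood will often already have been taken. Treatment before enrollment will still precede T0 in some patients, and its time should be recorded so that this can be described.
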